10.4.2 Pharmacodynamic Statistical Methodology

SARS-CoV-2 viral load

SARS-CoV-2 viral load will be measured using the cycle time (CT) from a polymerase chain reaction (PCR) assay. Higher CT values indicate a lower viral load.

SARS-CoV-2 viral load, including changes from baseline, will be summarized and plotted by treatment, and listed. Baseline is defined as the Day 1 predose assessment. Overlaying individual profiles of SARS-CoV-2 viral load data will also be presented graphically over time.

Changes from baseline in SARS-CoV-2 viral load data will be statistically analyzed using a mixed model for repeated measures (MMRM). The model will contain baseline as a covariate, treatment, day and treatment-by-day interaction as fixed effects, and subject as a random effect. The unstructured covariance matrix will be selected initially; if this analysis fails to converge another covariance structure will be selected based on AIC and BIC values. The least square (LS) means and treatment differences (LY3819253 minus pooled placebo at each dose level) will be calculated and presented with their corresponding 90% confidence intervals (CIs). All available data will be used in the analysis.

An example of the SAS code that will be used is as follows:

```
proc mixed data=xxx;
class trtmnt subject day;
model chg = base trtmnt day trtmnt*day / alpha=0.1 cl ddfm=kr2;
repeated day / subject=subject type=un;
lsmeans trtmnt*day / alpha=0.1 cl pdiff;
ods output lsmeans=lsm01 diffs=diff01;
run;
```

where chg is the change from baseline, base is the baseline in SARS-CoV-2 viral load data, day is the study day, and trtmnt is the treatment used in the comparison.

A Bayesian linear mixed effect model will be fitted to evaluate the critical success factor by Lilly statistics group with the model listed below:

 $y_{ijk} = \mu + \alpha \times base + \alpha_i + \beta_k + (\alpha\beta)_{ik} + \varepsilon_{ij} + \varepsilon_{ijk}$

Where y_{iik} : the change from baseline for treatment i, subject j at day k

μ: a constant common to all observations

 α : a fixed coefficient on the covariate baseline viral load

 $\alpha_{i:}$ a parameter corresponding to treatment i

 $\beta_{k:}$ a parameter corresponding to day k

 $(\alpha\beta)_{ik:}$ an interaction parameter corresponding to treatment i and day k

 ϵ_{ij} , ϵ_{ijk} : random error for between and within subject variability

prior μ , α , α_{i} , β_{k} , $(\alpha\beta)_{ik} \sim N(0, 100)$

 $\varepsilon_{ij} \sim N(0, \sigma_1), \ \varepsilon_{ijk} \sim N(0, \sigma_2)$

 $\sigma_{1}, \sigma_{2} \sim uniform(0, 100) \text{ or } igamma(0.01, 0.01)$

the posterior of the following quantity will be assessed:

 $pr(\Delta_{anyLYdose} - \Delta_{placebo} < -0.3) > 0.6 \text{ at Day 7, 11, 15, and 22 in log base 10 scale.}$

SARS-CoV-2 viral load AUC

The AUC from Day 1 predose to Day 29 (AUC[0-D29]) will be calculated according to the linear trapezoidal rule using the measured SARS-CoV-2 viral load-time values above the lower limit of quantification. No imputations of missing data will be conducted. No AUC(0-D29) values will be calculated when Day 1 predose and/or Day 29 values are missing, or if there are more than 3 values missing in the profile.

The AUC(0-D29) will be summarized and plotted by treatment and listed.

Additionally, AUC(0-D29) data will be statistically analyzed using a linear model. The model will contain treatment as a fixed effect and baseline viral load as a covariate. The least square (LS) means and treatment differences (LY3819253 minus pooled placebo at each dose level) will be calculated and presented with their corresponding 90% confidence intervals (CIs). All available data will be used in the analysis.

An example of the SAS code that will be used is as follows:

```
proc mixed data=xxx;
class trtmnt;
model AUC = base trtmnt / alpha=0.1 cl ddfm=kr2;
lsmeans trtmnt / alpha=0.1 cl pdiff;
ods output lsmeans=lsm01;
ods output diffs=diff01;
run;
```

where AUC is the AUC(0-D29) data, trtmnt is the treatment used in the comparison, and base is the baseline viral load.

Similar Bayesian model listed in Section 10.4.2 by removing the day, interaction, and within subject error term will be applied for AUC measure analysis.

SARS-CoV-2 clearance

The proportion of patients that achieve SARS-CoV-2 clearance will be summarized by treatment in frequency tables, and listed.

In addition, the number of patients that achieve SARS-Cov-2 clearance will be analyzed using a Chi-square test to compare LY3819253 versus pooled placebo at each dose level, if there are sufficient data available.

An example of the SAS code that will be used is as follows:

```
proc freq data=xxx;
weight count;
table trtmnt*clear / chisq all;
run;
```

where trtmnt is the treatment used in the comparison, clear is the SAR-CoV-2 clearance (yes/no), and count is the corresponding number of patients.

Additional analyses on viral clearance, such as logistic regression with treatment as a fixed effect, may be conducted as deemed appropriate and where sufficient data are available.

Time to SARS-CoV-2 clearance

The time to SARS-CoV-2 clearance will be summarized by treatment, and listed.

In addition, a graphical presentation of the clearance times will be provided using a Kaplan-Meier plot.

Viral Resistance to LY3819253

Participant who show signs of viral resistance will be summarized in frequency tables by treatment and listed.

PK/PD Modeling

Additional PK/PD exposure-response modeling of viral dynamics may be conducted. These analyses will be the responsibility of Eli Lilly PK/PD group.

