6. STUDY DESIGN

Study PYAA is a Phase 1, double-blind, sponsor unblinded, randomized, placebo-controlled, single-ascending dose study in participants hospitalized for COVID-19.

The study will comprise up to 4 dose cohorts. Cohorts 1-3 will compromise at least 8 participants:

- 6 randomized to LY3819253 and
- 2 randomized to placebo.

Sentinel dosing will be used in any dose cohort that represents a dose increase from the preceding cohort. The first 2 participants in each cohort will be randomized 1:1 to LY3819253 and placebo.

Safety and tolerability will be reviewed for sentinel participants up to 24 hours after dosing. The investigator and the Lilly sponsor team are responsible for determining if safety and tolerability is acceptable to continue with dosing subsequent participants. Subsequent participants will be randomized to the remaining treatment allocations, 5 to LY3819253 and 1 to placebo.

The decision to dose the next cohort will be made when all participants from the previous cohort have been dosed and safety data is assessed for at least 4 days after the IV infusion by the investigator(s) and Lilly sponsor team in consultation with an independent safety assessment committee (ISAC).

Cohort 4 may be initiated, at the discretion of the sponsor team, if more data is needed to inform

Figure 1 - Sequential single ascending dose schema of study J2W-MC-PYAA

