7. TREATMENTS

Cohort	Study Treatment Name*	Treatment order in TFL
All	Pooled placebo IV	1
1	700 mg LY3819253 IV	2
2	2800 mg LY3819253 IV	3
3	7000 mg LY3819253 IV	4
4 (optional)	TBD mg LY3819253 IV	5

The following is a list of the study treatment abbreviations that will be used in the TFLs.

Abbreviations: IV = intravenous; TBD = to be determined.

* Planned doses presented - the actual dose administered will be displayed in the TFLs.

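### One baseline slope for all days in the viral-load MMRM and Bayesian model leaves chance baseline imbalance only partly removed at 6 per arm; a baseline-by-day term fixes this cheaply

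*SAP*

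**What the plan says.** SAP 10.4.2 specifies the analysis of change from baseline in viral load in three places, and baseline enters once in each.

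- MMRM text: "The model will contain baseline as a covariate, treatment, day and treatment-by-day interaction as fixed effects, and subject as a random effect".
- Example SAS code: "model chg = base trtmnt day trtmnt*day / alpha=0.1 cl ddfm=kr2", with an unstructured covariance over days within subject.
- Bayesian model: the baseline term is "a fixed coefficient on the covariate baseline viral load" and carries no day index. The treatment effect does have a day-specific part, "an interaction parameter corresponding to treatment i and day k". Within-subject correlation comes from a subject-level error plus a residual error.

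The Bayesian model is judged day by day. The posterior probability that a dose-minus-placebo difference lies below -0.3 must exceed 0.6, "at Day 7, 11, 15, and 22 in log base 10 scale". The MMRM has no threshold and is reported with 90% confidence intervals.

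Arms are small. SAP section 6 gives each of Cohorts 1-3 "6 randomized to LY3819253 and" "2 randomized to placebo". SAP section 7 lists one comparator, "Pooled placebo IV", so each dose of 6 is compared with 6 placebo participants before any Cohort 4.

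**The concern.** The baseline covariate is there to remove chance differences in starting viral load between small arms. It does this on a given day only if the fitted slope is right for that day.

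For a change score the slope should move over time. Once a swab is at the assay floor, change equals floor minus baseline, so the slope is -1 by arithmetic. At early visits, when most participants still have measurable virus, it can be much closer to zero. A single fitted slope is a compromise: too steep for Day 7 and too shallow for Day 22. A dose arm that starts with more virus than placebo then looks worse than it should on Day 7 and better than it should on Day 22.

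Change in viral load on these days is a secondary endpoint, and the sponsor will read the Bayesian result against a margin of only 0.3 log10.

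**Working it through.** **What the plan lets one reproduce.** No document states a figure for this issue. The greater-than-90% assurance in SAP section 8 concerns viral-load AUC and rests on a PK/PD model whose parameters are not given, so it cannot be reproduced. Its 0.3 is a 30% proportional reduction, not 0.3 log10. The arm size of 6 is confirmed by the safety statement in the same section: 1 - 0.75^6 = 0.822, above the stated 80%.

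**Inputs from the documents.** 6 v 6 for each dose comparison; up to 50 v 56 for a full Cohort 4 (56 = 50 + 6); Days 7, 11, 15 and 22; threshold 0.3 log10.

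**Assumptions, because the documents give no values.** Baseline SD 1 to 2 log10; day-specific slopes as listed below; complete data; no drug effect.

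**Formula.** Let b_k be the true slope of change on baseline at day k, b_c the common fitted slope, and D the baseline mean difference between two arms. With no drug effect the expected change difference is b_k x D, and the model subtracts b_c x D:

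shift on day k = (b_k - b_c) x D.

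For the random-subject (Bayesian) structure with vague priors, b_c is the simple average of the b_k. For the unstructured MMRM it is a weighted average.

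**Size of D.** SE(D) = SD x sqrt(1/6 + 1/6) = 0.58, 0.87, 1.15 log10 for SD 1, 1.5, 2. The chance that |D| exceeds 1 log10 is 8%, 25%, 39%.

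**Chance that |shift| exceeds 0.3 log10, 6 v 6**

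| b_k - b_c | D needed | SD 1 | SD 1.5 | SD 2 |
|---|---|---|---|---|
| 0.1 | 3.0 | 0% | 0.1% | 1% |
| 0.2 | 1.5 | 1% | 8% | 19% |
| 0.3 | 1.0 | 8% | 25% | 39% |
| 0.4 | 0.75 | 19% | 39% | 52% |
| 0.5 | 0.6 | 30% | 49% | 60% |

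**Assumed slope patterns over the four days, random-subject structure, |D| above 1 SE (SD 1.5 / SD 2)**

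- Equal slopes: about 0 on every day.
- Mild, -0.5 to -0.8: Day 7 +0.20 / +0.26; Day 22 -0.20 / -0.26.
- Moderate, -0.40 to -0.94: Day 7 +0.40 / +0.50; Day 22 -0.32 / -0.42.
- Steep, -0.2, -0.5, -0.84, -1.0: Day 7 +0.57 / +0.77; Day 22 -0.48 / -0.63.

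Hand check of the steep Day 7 value at SD 1.5: b_c = -2.54/4 = -0.635; departure = -0.2 + 0.635 = 0.435; mean |D| beyond 1 SE = 0.87 x (0.2420/0.1587) = 1.32; product 0.57. Averaged over all randomizations the mean error is at most 0.014 in every pattern, which is simulation noise.

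**Slopes generated from assumed viral kinetics.** Decline 0.25 log10/day (SD 0.08), 2-14 days since onset, peak 8 log10 (SD 1), floor 2 log10, swab noise SD 0.5, 1.0 or 1.5. |D| exceeds 1 log10 in about 25-40% of comparisons, rising with noise. Given that, the mean Day 7 shift at three noise levels in one run of this kind is:

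| Model | Visits | Day 7 shift |
|---|---|---|
| MMRM, unstructured | six (Days 3-29) | 0.51 / 0.52 / 0.42 |
| MMRM, unstructured | four endpoint days | 0.35 / 0.41 / 0.35 |
| Random-subject (Bayesian type) | four endpoint days | 0.35 / 0.29 / 0.25 |
| With baseline-by-day term | either | about 0 |

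Runs that differ in detail, such as how noise meets the floor, move these values: up to 0.68 for the six-visit MMRM and down to 0.17 for a six-visit random-subject fit. For the six-visit random-subject fit, Day 22 was -0.43 / -0.30 / -0.21.

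**Cohort 4.** At 50 v 56 the chance of |shift| above 0.3 is at most 1% for departures up to 0.3, and at most 12% overall (departure 0.5, SD 2). A 6-person dose arm against 56 pooled placebo benefits less: at departure 0.3 the chance is 12% (SD 1.5) or 24% (SD 2), against 25% or 39% at 6 v 6.

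**The case against.** A reader might infer that both planned analyses are biased by more than the decision threshold. The documents do not support that.

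- They give no baseline SD, no day-specific slopes and no CT-to-log10 conversion, so every size above is assumed.
- The error depends on the imbalance that happens to occur. By the kinetic runs, 60-75% of comparisons have no imbalance above 1 log10.
- The -0.3 rule belongs to the Bayesian model, where the shift is about at the threshold. The larger shifts are in the unstructured MMRM, which has no threshold, and partly reflect including Days 3 and 29. SAP 10.4.2 says all available data are used but does not list the visits in the model.
- The rule's overall behaviour hardly changes. With no drug effect, one dose meets the Day 7 criterion in 20/27/29% of simulated trials with the common slope and 19/26/29% with day-specific slopes. For any dose on any of the days the figures are 70/77/82% and 64/74/83%. The 0.6 cut-off and n = 6 dominate.
- Protocol 9.1 calls treatment comparisons exploratory, raw changes and individual profiles are also shown, and the escalation criteria in Protocol 6.6.1 do not rest on this contrast.

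All of this stands and limits the weight of the point. It does not justify the single slope. The sponsor will interpret one realized imbalance, which the covariate is meant to remove, and the planned form does so incompletely unless slopes are equal across days.

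**Conclusion.** The point holds as a refinement. Both models impose one baseline slope on all days of a change score whose dependence on baseline is expected to strengthen as virus clears. The estimators are unbiased on average, so over repeated trials the cost is extra variance.

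At 6 v 6, and given an imbalance above 1 log10, early and late differences (Days 7 and 22) can shift by roughly 0.25-0.5 log10: about 0.35-0.5 at Day 7 for the unstructured MMRM and about 0.25-0.35 for the Bayesian model. That is comparable to the 0.3 log10 threshold. It is also set against a standard error of about 0.4 to 1.1 log10 for a 6 v 6 day-specific difference.

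These sizes rest on the assumed kinetics, a baseline SD of about 1.5-2 log10 and complete data. Mild slope changes give less (at most 0.26 in the pattern tested), an assumed steep pattern gives more, and equal slopes give none. Severity is low to moderate.

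**What to change.** In the MMRM, use `model chg = base day base*day trtmnt trtmnt*day` with the other options unchanged. In the Bayesian model, replace the single baseline coefficient with one per day (alpha_k x base) under the same prior. State which visits enter each model. If the team prefers to keep the planned models, report the day-specific version as a sensitivity analysis.

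The cost is one slope parameter per additional visit: three more with four visits, five more with six. If slopes are in fact equal, Day 7 RMSE rises only from about 0.80 to 0.82 (SD 1.5, 6 per arm). Under the steep pattern it falls from 0.65 to 0.53 on Day 7 and from 0.55 to 0.45 on Day 22. No new data are needed.

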9.1. Statistical Hypotheses

This is an exploratory study with a primary objective of assessing safety and tolerability. Any hypothesis tests conducted for treatment comparisons will be exploratory in nature and conducted without adjustment for multiplicity.

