9.2. Sample Size Determination

For Cohorts 1 - 3, approximately 24 participants will be randomized to receive one of three dose levels of LY3819253 or placebo. Additional participants may be required to ensure a minimum of 8 participants in each cohort complete 7 days of study assessments. Up to a maximum of 3 additional participants per cohort may be added.

Participant viral loads over time were simulated using a representative PK/PD model to enable a Monte Carlo assessment of the power of the trial to detect a 30% treatment difference in mean AUC (28 day) of viral load. This assessment revealed greater than 90% probability of meeting the following Bayesian critical success factor:

Pr ((mean AUC_{PL} – mean AUC_{LY})/ mean AUC_{PL} > 0.3) > 0.60 PL = placebo, LY = LY3819253

Additionally, the anticipated 6 participants per treatment provides greater than 80% probability (within each treatment arm) of observing safety events of reasonable prevalence (that is, at least 25%) to support the primary objective of safety assessment.

For the optional Cohort 4, up to 100 participants may be randomized in an approximate 1:1 ratio to receive either LY3819253 or placebo. The overall numbers of participants randomized to LY3819253 and placebo in this study will provide 60% power to detect a reduction in the rate of clinical worsening from 22% to 9% (one-sided alpha=0.05). Clinical worsening is defined as the proportion (percentage) of participants with any worsening on the NIAID ordinal scale from baseline to Day 15.

A participant is only allowed to receive one IV infusion in one cohort.

9.3. **Populations for Analyses**

This table defines the populations for analysis.

Population	Description
Entered	All participants who sign the informed consent form
Safety	All participants randomly assigned and who received study intervention.
	Participants will be analyzed according to the intervention they actually
	received.
Pharmacokinetic	All randomized participants who received study intervention and have
	evaluable PK sample. Participants will be analyzed according to the
	intervention they actually received.
Pharmacodynamic	All randomized participants who received study intervention and provided at
	least one post-baseline measure for the relevant endpoint. Participants will be
	analyzed according to the intervention they actually received.

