8. SAMPLE SIZE JUSTIFICATION

For Cohorts 1-3, approximately 24 participants will be randomized to receive one of three dose levels of LY3819253 or placebo. Additional participants may be required to ensure a minimum of 8 participants in each cohort complete 7 days of study assessments. Up to a maximum of 3 additional participants per cohort may be added.

Participant viral loads over time were simulated using a representative PK/PD model to enable a Monte Carlo assessment of the power of the trial to detect a 30% treatment difference in mean AUC (28 day) of viral load. This assessment revealed greater than 90% probability of meeting the following Bayesian critical success factor:

Pr ((mean AUC_{PL} – mean AUC_{LY})/ mean AUC_{PL} > 0.3) > 0.60

PL = placebo, LY = LY3819253

Additionally, the anticipated 6 participants per treatment provides greater than 80% probability (within each treatment arm) of observing safety events of reasonable prevalence (that is, at least 25%) to support the primary objective of safety assessment.

For the optional Cohort 4, up to 100 participants may be randomized in an approximate 1:1 ratio to receive either LY3819253 or placebo. The overall numbers of participants randomized to LY3819253 and placebo in this study will provide 60% power to detect a reduction in the rate of clinical worsening from 22% to 9% (one-sided alpha=0.05). Clinical worsening is defined as the proportion (percentage) of participants with any worsening on the NIAID ordinal scale from baseline to Day 15.

A participant is only allowed to receive one IV infusion in one cohort.

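### SAP 10.4.2 applies the name critical success factor to a -0.3 log10 rule at four visits, while SAP 8 defines the factor as a 30% lower mean 28-day viral load AUC, and the Bayesian AUC model has no success rule

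*SAP*

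**What the plan says.** **The factor as planned.** Protocol 9.2 describes a Monte Carlo assessment of the trial's power to "detect a 30% treatment difference in mean AUC (28 day) of viral load". It writes the criterion as Pr((mean AUC placebo - mean AUC LY) / mean AUC placebo > 0.3) > 0.60. SAP 8 repeats it: "This assessment revealed greater than 90% probability of meeting the following Bayesian critical success factor". Neither section says which dose comparison or which AUC scale was simulated.

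**The factor as analysed.** SAP 10.4.2, under viral load, states: "A Bayesian linear mixed effect model will be fitted to evaluate the critical success factor by Lilly statistics group". The response in that model is change from baseline in viral load by treatment, subject and day. After the priors, the SAP says "the posterior of the following quantity will be assessed". The quantity is the probability that the difference between any LY dose and placebo is below -0.3, required to exceed 0.6, "at Day 7, 11, 15, and 22 in log base 10 scale".

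**The AUC model.** Later in the same section: "Similar Bayesian model listed in Section 10.4.2 by removing the day, interaction, and within subject error term will be applied for AUC measure analysis". No threshold, probability cut-off or ratio is given for it.

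**Other relevant text.** SAP 10.4.2 says viral load is measured by PCR cycle time (CT), where a higher value means less virus. SAP 12 reports no changes from the protocol's analyses. Protocol 9.1 says: "Any hypothesis tests conducted for treatment comparisons will be exploratory in nature and conducted without adjustment for multiplicity".

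**The concern.** The SAP uses one name for two rules. The factor that supports the viral-load part of the Cohort 1-3 sample size is a relative difference in mean AUC. The rule written in the analysis section is a log10 difference at separate visits. An analyst who follows 10.4.2 literally would report the second under the name of the first, and would find no written rule to apply to the Bayesian AUC model.

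A pre-specified success criterion is useful only if the result reported under its name is that criterion. The shared name also invites a reader to attach the stated 90% probability to the visit rule, for which it was not computed.

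**Working it through.** **1. The plan's own figure.** The probability above 90% cannot be reproduced. The PK/PD model, the true effect and the variability behind it are not in the documents. The point does not depend on it.

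**2. The two rules side by side.**

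| | SAP 8 and Protocol 9.2 | SAP 10.4.2 |
|---|---|---|
| Endpoint | 28-day viral load AUC | change from baseline at Days 7, 11, 15, 22 |
| Quantity | relative difference in means | difference on log10 scale |
| Threshold | above 0.3 | below -0.3 |
| Posterior cut-off | 0.60 | 0.6 |

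Only the cut-off is shared.

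**3. What -0.3 means.** 10^(-0.3) = 0.501, so the visit rule concerns a 1 - 0.501 = 49.9% lower viral load. On the natural log scale it would be 1 - exp(-0.3) = 25.9%. Neither base gives 30%. A 30% reduction at a visit is log10(0.70) = -0.155. That value matches a 30% lower AUC only if the proportional effect is constant over the whole period and AUC is on the linear scale. The Day 1 sample is taken before dosing, so a drug effect cannot be present from the start of the AUC.

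**4. How a 50% lower load at the four visits maps to AUC.** Assumptions: linear-scale AUC by the trapezoidal rule on the scheduled swab days (1, 3, 7, 11, 15, 22, 29), placebo log10 decline of 0 to 0.3 per day, and load halved on LY3819253 from the stated day on.

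- *Flat placebo load, effect from Day 7.* Placebo AUC = 28. Loss from Day 3 to 7 = 4 × 0.5/2 = 1; from Day 7 to 29 = 22 × 0.5 = 11. Reduction = 12/28 = 43%.
- *Flat placebo load, effect already at Day 3.* Loss = 2 × 0.5/2 + 26 × 0.5 = 13.5. Reduction = 13.5/28 = 48%.
- *Decline 0.3 per day.* Placebo AUC = 1.821 (Day 1 load = 1), mostly accrued before Day 7. Reduction = 0.034/1.821 = 2% with effect from Day 7, and 0.411/1.821 = about 22% with effect from Day 3.

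The ranges are therefore 2% to 43% (from Day 7) and 22% to 48% (from Day 3). They span 30%, so the visit rule can be looser or stricter than the AUC rule.

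**5. Illustration of the visit rule's own behaviour.** The documents give no SD or correlation, so these are assumed: SD of change 0.5 to 1.5 log10, within-person correlation 0.5 to 0.7, three doses of 6 against 6 pooled placebo (SAP 7 lists "Pooled placebo IV" across all cohorts), and a near-flat prior with SD taken as known. The rule passes at a visit if the estimate is below -0.3 - 0.2533 × SE, with SE = SD × sqrt(1/6 + 1/6) = 0.289, 0.577 and 0.866 for SD 0.5, 1.0 and 1.5. If one reads it as the same dose passing on all four days, for any dose, simulation gives:

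- no true effect: 2% to 23%;
- a true 30% reduction at every dose and day: 10% to 30%;
- a true 50% reduction: 27% to 37%.

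These rates describe one reading under assumed inputs. They neither test the 90% figure nor measure the mislabelling.

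**The case against.** **The AUC factor has not been lost.** This stands. SAP 8 holds the rule and 10.4.2 plans a Bayesian AUC model, so the factor can still be evaluated. What is missing is the link: the AUC model has no rule, and the name sits on the other one.

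**Nothing depends on it.** This also largely stands. Tests are exploratory and unadjusted (Protocol 9.1). PD data may be used to guide dose adjustment (Protocol 6.6.1), but no passage makes escalation, stopping or Cohort 4 depend on the factor. The primary objective is safety.

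**SAP 12 is not shown to be false.** The protocol states the factor only under sample size. Protocol 9.4.3 plans descriptive PD summaries, and Protocol 9.4 lets changes that do not touch a principal feature be described in the SAP. The firm contradiction is SAP 8 against SAP 10.4.2; the silence in SAP 12 is secondary.

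**No joint pass/fail is written.** The text can equally be read as a separate posterior at each day and dose, which would match the by-day, by-dose differences from the repeated-measures model. The subscript for any LY dose and the list of days lean towards a joint reading but do not state it. The pass rates in step 5 do not apply under the separate reading.

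**Stronger readings a reader might infer.** One is that the SAP roughly doubled the hurdle, because -0.3 is about twice -0.155. That comparison needs a constant effect and linear-scale AUC, and step 4 shows the relation can go either way. Another is that the plan claims a probability above 90% for the visit rule; no passage does.

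**Conclusion.** The SAP is wrong as written on this point: it sets out to evaluate the critical success factor with a rule that is not the factor defined in its own section 8, and gives the AUC model no success rule. This follows from the text alone and needs no assumption. That -0.3 log10 is a 50% lower load at a visit is arithmetic. How it compares with a 30% lower AUC rests on the assumed decline, onset and AUC scale in step 4, and has no fixed direction. The stated 90% applies to the AUC rule only.

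The consequence is limited to exploratory reporting of the viral result, so this should be fixed but is of low priority. The documents do not support concluding that the planned factor was abandoned, that dose decisions are compromised, or that the 90% figure is incorrect.

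**What to change.** In SAP 10.4.2:

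- Write the section 8 posterior rule under the Bayesian AUC model and name it the critical success factor. Use, and state, the AUC scale and dose comparison of the simulation behind the 90% figure.
- Relabel the -0.3 rule as a separate supportive criterion: a 50% reduction in viral load, i.e. -0.3 log10.
- State how CT is converted to log10 viral load. Because higher CT means less virus, a difference below -0.3 indicates benefit only after that conversion.
- State whether the supportive rule is read separately by day and dose or jointly, and note the rule in SAP 12.
- Do not attach the 90% figure to it unless its own success probability is simulated.

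The cost is minor rewording and possibly one simulation run, with no change for participants or procedures. The downside is that any restated probability may be less favourable.
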